## 4.4.1.1 Supplemental Analyses

The following supplemental analyses will be performed for the primary efficacy endpoint to evaluate the robustness of the primary analysis finding:

a) Trimmed Mean Analysis: The analysis will be used to assess the difference in BVCA between two treatments using a truncated distribution, truncating patients with the worst outcome, with the assumption that patients have the worst outcome after intercurrent events.

The estimand is defined as follows:

- Population: Adult patients with nAMD diagnosed within 9 months and receiving at least 4 anti-VEGF intravitreal injections (with the last injection being ranibizumab) responsive to prior anti-VEGF treatment
- Variable: Change in BCVA score from baseline averaged over Weeks 36 and 40
- Intercurrent events: Assume patients have the worst outcome after the following intercurrent events prior to Week 40:
  - -Receives more than 1 supplemental treatment
  - -Receives any prohibited systemic treatment or prohibited therapy in the Study eye (Section 4.4.2 of the Protocol)
  - Discontinues study treatment due to AEs
  - Discontinues study treatment due to lack of efficacy as per investigator's clinical judgment
- Population-level summary: Difference in adjusted trimmed mean between PDS
   100 mg/mL and intravitreal groups

The trimmed mean analysis (Permutt and Li 2017) will be performed using an analysis of covariance (ANCOVA) model with adjustment for covariates. The dependent variable in the ANCOVA model is the average of non-missing values of Weeks 36 and 40

assessments in change from baseline in BCVA score (if one of the two assessments is missing, the non-missing assessment will be used), and the independent variables are the treatment group, baseline BCVA score (continuous), and the randomization stratification factor of baseline BCVA (<74 letters vs.≥74 letters).

Patients will be considered to have the worst outcomes and will be trimmed from analysis if any of the following occurs:

- They have an intercurrent event prior to Week 36.
- They have a missing Week 36 assessment and have an intercurrent event at Week 36.
- They have missing assessments at both Week 36 and Week 40, and have an intercurrent event in either of these two visits.

Such patients will be referred to as "must be trimmed patients". Of note, if a patient has a non-missing Week 36 assessment and has an intercurrent event at Week 36, then the change in BCVA from baseline to Week 36 for this patient will be used for the analysis, the Week 40 data would not be used.

For the remaining patients, if they have Week 36 and/or Week 40 BCVA assessments, they will be considered "completers"; if they have missing assessments at both Week 36 and Week 40, the missing data will be considered missing at random and these patients will be removed from the analysis.

The inferential statistics (i.e., 95.03% CI) for the trimmed mean will be based on the permutation test. The treatment assignments will be permuted in a sufficiently large random sample of possible ways (~30,000 random samples will be generated).

The method can be stated in the following four steps:

- 1. Remove patients whose missing BCVA assessments are considered missing at random (see definition above) from the analysis.
- Order the data based on adjusted values from the ANCOVA model, and trim equal fractions (approximately 20%, the trimming fraction will be finalized based on a masked assessment prior to the primary analysis) from both treatment groups.
  - The adjusted values are determined as follows. An ANCOVA model as specified above will be fitted for all completers. The estimated treatment effect will be discarded and the coefficients for the covariates will be kept to calculate the adjusted value Y − β' X for each patient, for which Y is the change in BCVA score averaged over 36 and 40 weeks, X is the matrix for the covariates-baseline BCVA score (continuous) and the baseline BCVA category (< 74 letters vs. ≥ 74 letters), and β is the estimated coefficient matrix for the covariates.

  - These adjusted values will be used to rank the data within each treatment group. The "must be trimmed" patients will always be ranked the lowest

(regardless of whether their adjusted values are available) and trimmed from the analyses. The best  $(1-0.2) \times 100$  (=80%) in each group will be used for the analysis specified in Step 3. If multiple patients have the same adjusted values, they will be ranked randomly relative to each other prior to trimming.

- 3. Refit the ANCOVA model (as specified above) to the trimmed data set, and compute the difference in trimmed mean between two treatment groups.
- 4. Repeat steps 2 and 3 30,000 times based on augmented datasets with the treatment assignment randomly permuted according to the original randomization procedures (blocked randomization stratified by baseline BCVA category).

When the proportion of the "must be trimmed patients" in either treatment group in the permuted data exceeds the planned trimmed fraction, the trimming fraction will be chosen adaptively as the greater of the proportions of the "must be trimmed patients" in the two treatment groups.

b) Analyses using different handling rules for intercurrent event

The estimand is defined as follows:

- Population: Adult patients with nAMD diagnosed within 9 months and receiving at least 4 anti-VEGF intravitreal injections (with the last injection being ranibizumab), responsive to prior anti-VEGF treatment
- Variable: Change in BCVA score from baseline averaged over Weeks 36 and 40
- Intercurrent events prior to Week 40:
  - Had more than 1 supplemental treatment not been made available
  - Had any prohibited systemic treatment or prohibited therapy in the Study eye (Section 4.4.2 of the Protocol) not been made available
  - Regardless whether a patient discontinues study treatment due to AEs
  - Regardless whether a patient discontinues study treatment due to lack of efficacy as per investigator's clinical judgment
- Population-level summary: Difference in adjusted mean between PDS 100 mg/ml and intravitreal groups

Two analyses will be performed using the same analysis method as the primary endpoint with the exception that data handling methods for intercurrent events and missing data:

Method 1: Assessments at any timepoint after 2 or more supplemental treatments or after prohibited treatments in the study eye will be imputed using the last post-baseline observation prior to such intercurrent event. This means for example that if a patient has their first intercurrent event at Week 36 or between the Week 36 and Week 40, the Week 36 assessment will be used for Week 40 (BCVA assessment will be performed before any treatment). Other missing assessments

- not preceded by an intercurrent event will be imputed using the last post-baseline observation carried forward method.
- Method 2: Assessments after 2 or more supplemental treatments or after prohibited treatment will be excluded. All missing data will be implicitly imputed by the MMRM model, assuming a missing at random mechanism.

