# 4.4.2.1 Key Secondary Endpoints for EMA

The following endpoints are considered key secondary endpoints for purpose of the marketing authorization application for EMA:

- Change from baseline in BCVA score averaged over Week 36 and Week 40
- Change from baseline in BCVA score averaged over Week 44 and Week 48
- Change from baseline in BCVA score averaged over Week 88 and Week 92

The hypothesis testing for these endpoint will be gated on achieving NI for the primary endpoint test at a 4.5 letter margin as per Section 4.4.1. A fixed sequence testing

procedure will be used to control the type I error rate. The NI tests for the key secondary endpoints will be performed in the order shown above with a NI margin of 3.9 letters, proceeding sequentially and testing each after achieving NI on the previous endpoint. Analysis of these key secondary endpoints will follow the same method as the analysis of the primary endpoint (see Section 4.4.1) in all respects except for the NI margin and timepoints included in the analysis. The two supplementary analyses for using different handling rules for intercurrent events (Section 4.4.1.1) and the per protocol sensitivity analysis (Section 4.4.1) used in the analysis of the primary endpoint will also be conducted for the key secondary endpoints.

Additionally, to address feedback from the EMA, sensitivity analyses will be conducted for each of the above 3 endpoints based on the complete cases in the Per Protocol Population. These analyses include only patients in the Per Protocol Population with BCVA assessments available at both study visits for a particular endpoint (e.g., patients needed to have BCVA assessments at both Weeks 36 and 40 for change in BCVA averaged over Weeks 36 and 40). The analyses will be conducted using the MMRM model as specified in Section 4.4.1, , and using the ANCOVA models with adjustment of treatment group, baseline BCVA score (continuous), and the randomization stratification factor of baseline BCVA (< 74 letters vs. ≥ 74 letters).

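### Does reusing the Week 36/40 supplementary analyses at Weeks 44/48 and 88/92 leave it open which patients have an intercurrent event?

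*SAP*

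**What the plan says.** Part (b) of SAP 4.4.1.1 defines one hypothetical estimand and two ways to estimate it. The estimand's variable is the Week 36/40 average, and directly below it the event list is headed "Intercurrent events prior to Week 40". Besides more than one supplemental treatment, the list covers prohibited medication in these terms: "Had any prohibited systemic treatment or prohibited therapy in the Study eye", with a reference to Protocol 4.4.2.

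The Methods are worded differently. Method 1, which carries the last pre-event value forward, says "Assessments at any timepoint after 2 or more supplemental treatments or after prohibited treatments in the study eye will be imputed". Method 2, which leaves later values to the MMRM, says "Assessments after 2 or more supplemental treatments or after prohibited treatment will be excluded".

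SAP 4.4.2.1 lists three key secondary endpoints for the EMA. The first repeats Weeks 36/40. The others are "Change from baseline in BCVA score averaged over Week 44 and Week 48" and "Change from baseline in BCVA score averaged over Week 88 and Week 92". Their main analysis follows SAP 4.4.1 "in all respects except for the NI margin and timepoints included in the analysis". The next sentence says that the two part (b) analyses will be run for these endpoints too. It restates neither the event window nor the list of prohibited treatments.

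**The concern.** Two things look unsettled.

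**Window.** Taken literally, the estimand ignores any event from Week 40 onward, even for an endpoint at Weeks 88/92. Supplemental injections at Weeks 40, 44, 64, 68 and 88 would then never count. The Method text has no such limit. Supplemental treatment exists only in the implant arm, so for that event the choice alters implant-arm data only. Prohibited treatment started late raises the same question in both arms.

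**Scope.** The estimand names systemic treatment and study-eye therapy, Method 1 only the study eye, and Method 2 no site. A patient given only a systemic anti-VEGF agent has an event under the estimand but not under Method 1's words.

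At stake would be reproducibility. Two programmers could build different Week 88/92 data sets, and a gap between the two Methods could come from different event sets instead of from the different handling of later values.

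**Working it through.** The SAP states no figure on this point, so there is none to reproduce. The check has three steps.

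**1. Where the window readings differ.** Supplemental treatment is possible at Weeks 16, 20, 40, 44, 64, 68, 88 and 92 (SAP 2), and BCVA is measured before any treatment at a visit (SAP 4.4.1.1). With n supplemental visits before an assessment, C(n,2) pairs of injections can trigger under a moving window. Under a fixed Week 40 limit only the pair 16 and 20 can.

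| Assessment | n | Pairs, Week 40 limit | Pairs, moving window |
|---|---|---|---|
| Week 36 or 40 | 2 | 1 | 1 |
| Week 44 | 3 | 1 | 3 |
| Week 48 | 4 | 1 | 6 |
| Week 88 | 6 | 1 | 15 |
| Week 92 | 7 | 1 | 21 |

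The readings agree at Weeks 36/40 and separate afterwards.

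**2. How much it could matter.** Assume a constant, independent probability p of supplemental treatment per visit. The share of implant patients on whom the readings disagree is

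[1 − (1 − p)^n − n·p·(1 − p)^(n−1)] − p².

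At p = 5%, Week 88 gives 3.277% − 0.250% = 3.027%, and Week 92 gives 4.438% − 0.250% = 4.188%.

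| p (assumed) | Week 44 | Week 48 | Mean | Week 88 | Week 92 | Mean |
|---|---|---|---|---|---|---|
| 1% | 0.02% | 0.05% | 0.03% | 0.136% | 0.193% | 0.165% |
| 5% | 0.48% | 1.15% | 0.81% | 3.027% | 4.188% | 3.608% |
| 10% | 1.80% | 4.23% | 3.02% | 10.43% | 13.97% | 12.20% |

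The implant arm has about 418 × 3/5 = 250.8 patients. For p of 1% to 5% that is 0.3 to 7.6 patients at Week 88 and 0.5 to 10.5 at Week 92.

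If a carried value differs from the observed one by 5 to 10 letters (assumed, all in one direction), the implant-arm mean in Method 1 moves as follows:

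- Weeks 88/92: from 0.00165 × 5 = 0.008 to 0.03608 × 10 = 0.36 letters, or 0.2% to 9% of 3.9.
- Weeks 44/48: from 0.002 to 0.08 letters.
- At p = 10% and 10 letters: 0.1220 × 10 = 1.22 letters at Weeks 88/92 (31% of 3.9) and 0.30 at Weeks 44/48.

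The 10% row is a stress case. The nearest figure in the documents is from the Phase II study (Protocol 1.3.2), where 79.8% of the 100 mg/mL arm went at least six months without needing a refill. Spread over two visits that is 1 − √0.798 = 10.7% per visit. It rests on that study's refill criteria, which the documents do not list, so it does not estimate the rate here.

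**3. Which reading the SAP supports.**

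- The Week 40 limit follows a variable line that also names only Weeks 36 and 40. Reuse at Weeks 88/92 must replace the weeks in that line, and freezing the next one would be arbitrary.
- SAP 4.4.1 bases the primary MMRM on data up to Week 40. Carried over literally, Weeks 88/92 could not be estimated at all. SAP 4.4.2 instead fits the same model to Weeks 4 to 96 for the final report.
- Method 1 applies at any timepoint, and its worked example dates the event relative to the assessment being replaced.
- The binary secondary endpoints in SAP 4.4.2 date events relative to each endpoint's own visit.

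On scope, Method 1 carries forward the last value before the intercurrent event, and the estimand just above defines that event. Method 2's shorter phrase reads naturally as the same event. The one real omission is systemic treatment in Method 1. Of the eight items in Protocol 4.4.2, one is expressly systemic, and systemic anti-VEGF use already excludes a patient at entry (Protocol 4.1.2.4). One such patient with a 10-letter difference would move an arm mean by 10/250.8 = 0.04 letters (implant) or 10/167.2 = 0.06 letters (intravitreal).

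**The case for a change.** The strongest case for a change is that the moving window is inferred, never written for part (b). SAP 4.4.2 says the primary endpoint's intercurrent events and handling rules carry over to continuous secondary endpoints, and the primary list is also dated before Week 40. The allowance for different timepoints in SAP 4.4.2.1 sits in the sentence before the one that reuses part (b). Where the authors wanted a moving window, for the binary endpoints, they wrote one. On scope, two Methods serving one estimand should share one event definition word for word. Finally, a by-arm summary of intercurrent events is stated only for COVID-19 events (SAP 4.4.2.2).

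The wording slips stand: the window is not restated, and Method 1 drops the systemic item. The consequence does not. Carrying over the primary rules cannot mean freezing their weeks, because the same step would cap the data at Week 40. Nor would repeat rescue be hidden:

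- SAP 4.2 summarizes the number of supplemental injections, lists major deviations, and reports systemic, study-eye and fellow-eye medications separately.
- SAP 4.4.2 reports supplemental treatment between refill-exchanges.
- SAP 4.4.3 plots BCVA by patient with supplemental treatments marked.

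These outputs do not name the rule that was programmed, but affected patients could be counted from them. A further table would be a reporting preference.

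**Conclusion.** No change is needed. This is missing detail that an analyst would fill in the same way from the surrounding text: events count up to the endpoint's own visits, and both Methods use the estimand's event definition. The primary and key secondary non-inferiority tests include all observed values whatever the intercurrent events, so neither reading touches them. Methods 1 and 2 are supplementary and have no success criterion. The window readings coincide at Weeks 36/40, and the Primary and Update CSRs were complete when SAP version 3 was written, so the question is live only for the Week 88/92 supplementary results.

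There the readings differ by 0.01 to 0.36 letters under an assumed 1% to 5% per-visit rate and a 5 to 10 letter gap. A 10% rate, or rescue clustered in the same patients, would make that larger. The conclusion therefore rests mainly on the clear intended reading and the absence of any decision attached to these analyses, and less on the size. No rate is available for prohibited treatment.

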## 4.4.2 Secondary Efficacy Endpoints

Descriptive summaries will be provided for all secondary endpoints based on all observed data. The secondary endpoints are:

- 1. Change from baseline in BCVA score averaged over Week 60 and Week 64.
- 2. Change from baseline in BCVA score over time.
- 3. Proportion of patients with BCVA score of 38 letters (20/200 approximate Snellen equivalent) or worse at the average over Week 36 and Week 40.
- 4. Proportion of patients with BCVA score of 38 letters (20/200 approximate Snellen equivalent) or worse over time.
- 5. Proportion of patients with BCVA score of 69 letters (20/40 approximate Snellen equivalent) or better at the average over Week 36 and Week 40.
- 6. Proportion of patients with BCVA score of 69 letters (20/40 approximate Snellen equivalent) or better over time.
- 7. Proportion of patients who lose < 10 or < 5 letters in BCVA score from baseline to the average over Week 36 and Week 40.
- 8. Proportion of patients who lose < 10 or < 5 letters in BCVA score from baseline over time.
- 9. Proportion of patients who gain ≥0 letters in BCVA score from baseline to the average over Week 36 and Week 40.
- 10. Proportion of patients who gain ≥0 letters in BCVA score from baseline over time.
- 11. Change from baseline in CPT assessed by central imaging vendor with boundaries ILM to inner third of the retinal pigment epithelium (RPE) at Week 36.
- 12. Change from baseline in CPT assessed by central imaging vendor with boundaries ILM to inner third of the RPE over time.
- 13. Proportion of patients in the PDS 100 mg/ml group who undergo supplemental treatment of intravitreal ranibizumab before the first, second, third, and fourth fixed refill-exchange intervals.
- 14. Proportion of patients in the PDS 100 mg/ml group that undergo a supplemental treatment that requires at least one additional supplemental treatments during the study.

The estimand for the binary secondary endpoints are defined as follows:

- Population: Adult patients with nAMD diagnosed within 9 months and receiving at least 4 anti-VEGF intravitreal injections (with the last injection being ranibizumab), responsive to prior anti-VEGF treatment.
- Variable: Proportion of patients for event of interest
- Intercurrent events: Regardless whether or not a patient has the following intercurrent event prior to visit for endpoint:
  - Receives more than 1 supplemental treatments
  - Receives any prohibited systemic treatment or prohibited therapy in the Study eye (Section 4.4.2 of the Protocol)
  - Discontinuation study treatment due to AEs
  - Discontinuation study treatment due to lack of efficacy as per investigator's clinical judgment.
- Population-level summary: Difference in proportions between PDS 100 mg/ml and intravitreal groups

The proportion of patients in each treatment group and the overall difference in proportions between treatment groups will be estimated using the weighted average of the observed proportions and the differences in observed proportions over the strata defined by randomization stratification factor of baseline BCVA (< 74 letters vs. ≥ 74 letters) using the Cochran-Mantel-Haenszel (CMH) weights (Cochran 1954; Mantel and Haenszel 1959). All observed measurements will be included in the analysis regardless whether or not a patient has an intercurrent event. Confidence intervals of the proportion of patients in each treatment group and the overall difference in proportions between treatment groups will be calculated using the normal approximation to the weighted proportions (Mehrotra and Railkar 2000). If the response rate is low, an unstratified analysis may also be performed.

In addition, the binary secondary endpoints through Week 40 will also be summarized using the same approach with missing assessments imputed with the last post-baseline observation carried forward (continuous BCVA values are carried forward and then the binary endpoint is derived).

Different strata will be used for the CMH analyses of the following binary endpoint:

Proportion of subjects with a BCVA score of 69 letters (approximate 20/40 Snellen equivalent) or better at the average over Weeks 36 and 40: the difference between the two treatment groups will be estimated using the same approach stratified by baseline BCVA (Snellen equivalent of 20/40 or better vs. worse than 20/40).

The continuous secondary endpoints will be summarized using descriptive statistics based on all observed data. These continuous endpoints will also be analyzed following

the same method as the analysis of the primary endpoint (see Section 4.4.1) with the independent variable, baseline BCVA score (continuous), in the model replaced with the baseline value of the corresponding endpoint (e.g., baseline CPT). The intercurrent events and data handling rules for the primary endpoint will apply here.

The proportion of patients in the PDS 100 mg/ml group who undergo supplemental treatment of intravitreal ranibizumab and who do not undergo supplemental treatment will be summarized descriptively during the entire study period and between each refillexchange. The proportion of patients in the PDS 100 mg/ml group who undergo a supplemental treatment and require subsequent additional supplemental treatments during the study will also be summarized descriptively. The proportion of patients who undergo supplemental treatment will be evaluated using only the patients who were able to be assessed for the need for supplemental treatment. This is the subset of patients who were assessed for supplemental treatment at least once at eligible weeks within a given interval (at 4 and 8 weeks prior to the scheduled refill visit), which does not include those who missed both visits within a given interval or discontinued the study prior to these 2 visits within a given interval, as these patients are not able to be assessed for the need for supplemental treatment. The proportion of patients who undergo supplemental treatment during the entire study period will be evaluated using the subset of patients who were assessed for supplemental treatment at least once during the entire study period.

For the Final CSR analysis, the following secondary efficacy endpoints occurring after Week 48 will be analyzed using the same MMRM model as specified in Section 4.1.1, with the dependent variables of changes in BCVA at Weeks 4-96: change in BCVA averaged over Week 60 and Week 64, change in BCVA averaged over Week 88 and Week 92, and change in BCVA over time through Week 96. Composite contrasts will be used to estimate each endpoint. These endpoints will also be analyzed on the Per Protocol Population using the same MMRM approach. No data collected after Week 96 will be used to evaluate these efficacy endpoints. In addition, a small number of BCVA assessments were not assessed per protocol (e.g., completed by uncertified staff or by unmasked staff), and these records will be removed from the efficacy analyses, as these records may not be reliable assessments of BCVA.

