#### 6.4.2 Secondary Efficacy Endpoints

The continuous secondary endpoints will be summarized using descriptive statistics based on all observed data. These continuous endpoints will also be analyzed following the same method as the analysis of the primary endpoint (see Section 6.4.1) with the independent variable, baseline BCVA score (continuous), in the model replaced with the baseline value of the corresponding endpoint (e.g., baseline CPT). The intercurrent events and data handling rules for the primary endpoint will apply here. Descriptive summaries will be provided for all secondary endpoints based on all observed data. Baseline is defined as the last available measurement prior to first treatment.

Unless otherwise specified, for binary secondary endpoints, the proportion of patients in each treatment group and the overall difference in proportions between treatment groups will be estimated using the weighted average of the observed proportions and the differences in observed proportions over the strata defined by randomization stratification factor of baseline BCVA (< 74 letters vs. ≥ 74 letters) using the Cochran-Mantel-Haenszel weights (Cochran 1954; Mantel and Haenszel 1959). All observed measurements will be included in the analysis regardless whether or not a patient has an intercurrent event. Confidence intervals of the proportion of patients in each treatment group and the overall difference in proportions between treatment groups will be calculated using the normal approximation to the weighted proportions (Mehrota and Railkar 2000). If the response rate is low, an unstratified analysis may also be performed.
The secondary efficacy endpoint, proportion of patients who undergo supplemental treatment, will be evaluated using only the patients who were able to be assessed for the need for supplemental treatment. The analysis will exclude any patients who discontinued treatment before the refill-exchange planned visit or who missed both refill-exchange visits, as these patients are not able to be assessed for the need for supplemental treatment. The unadjusted proportion of patients who undergo supplemental treatment as well as of patients who do not undergo supplemental treatment will be reported.

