The dependent variable in the MMRM model is the change from baseline in BCVA score at post-baseline visits, up to 40 weeks, and the independent variables are the treatment group, time, treatment-by-time interaction, baseline BCVA score (continuous), and the randomization stratification factor of baseline BCVA (<74 letters vs.≥74 letters) as fixed

effects. The MMRM model will assume an unstructured covariance structure. If there are convergence problems with the model, then a compound symmetry covariance or a first order autoregressive order (AR [1]) covariance structure will be used. Comparisons between the two treatment groups will be made using a composite contrast over Weeks 36 and 40.

For the primary efficacy endpoint, if a lower bound of a two-sided 95.03% CI for the difference of two treatments is greater than -4.5 letters (the NI margin), then treatment via PDS is considered non-inferior to monthly intravitreal ranibizumab treatment. If the two-sided 95.03% CI is within -4.5L and +4.5L, then the two treatment regimens are considered clinically equivalent.

As a sensitivity analysis the per-protocol analysis will follow the same methods as the primary analysis except the Per-Protocol Population will be used.

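### The 69-letter (20/40 or better) endpoints adjust for baseline only through a two-level split; using the continuous baseline score would tighten their confidence intervals slightly at almost no cost

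*SAP*

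**What the plan says.** SAP 4.4.2 defines the summary for binary secondary endpoints as "Population-level summary: Difference in proportions between PDS 100 mg/ml and intravitreal groups". It estimates that difference over "strata defined by randomization stratification factor of baseline BCVA (< 74 letters vs. ≥ 74 letters"), "using the Cochran-Mantel-Haenszel (CMH) weights" and a normal-approximation interval. Protocol 6.4.2 describes the same estimator ("using the weighted average of the observed proportions and the differences in observed proportions over the strata").

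Two listed endpoints use the 69-letter threshold:

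- **Week 36/40 average.** This endpoint alone gets different strata; it is "stratified by baseline BCVA (Snellen equivalent of 20/40 or better vs. worse than 20/40").
- **Over time** ("Proportion of patients with BCVA score of 69 letters (20/40 approximate Snellen equivalent) or better over time"). No exception is made, so the default 74-letter split applies.

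The only alternatives offered for binary endpoints are a last-observation-carried-forward version through Week 40 and a possible unstratified analysis if the response rate is low. By contrast, the primary MMRM in SAP 4.4.1 includes "time, treatment-by-time interaction, baseline BCVA score (continuous), and the randomization stratification factor of baseline BCVA". The trimmed-mean ANCOVA (SAP 4.4.1.1) and the complete-case ANCOVA (SAP 4.4.2.1) also use both terms.

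**The concern.** Whether a patient ends at 69 letters or better depends heavily on the starting score. A two-level split treats everyone on one side of the cut as alike. Eligibility starts at 34 letters, so the lower stratum mixes patients with very different chances of reaching the threshold. The 74-letter split also puts patients who start at 69-73, already at or past the threshold, with those who start well below it.

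What is at stake is precision. SAP 4.4 promises an estimate and a 95.03% CI for these endpoints, and in a non-inferiority and equivalence trial readers use such intervals to judge how large a loss of useful vision can be excluded. An interval wider than the collected data require is an avoidable, if small, cost.

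**Working it through.** **The plan's own figure.** The plan gives no expected rate or power for the 69-letter endpoints. Its only power statement is for the primary endpoint, and it reproduces. With SD 9.5, difference -0.75, margin 4.5 and one-sided 0.025, 216 + 144 patients give 95.5% for both non-inferiority and equivalence. After both 10% allowances (0.9 × 0.9 = 0.81 of the sample) this becomes 90.9% and 90.4%, against the stated minimum of 90%.

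**Inputs from the documents.** Threshold 69 letters; strata cut at 20/40 (taken as 69 letters) or at 74; change SD 9.5 (SAP 2.2); 418 patients at 3:2, so 418 × 0.6 ≈ 251 and 418 × 0.4 ≈ 167; 95.03% CI, z = 1.963; eligibility floor 34 letters.

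**Assumed, because the documents do not give it.** Baseline B is normal with mean 70-76 and SD 8-14, restricted to 34-100 letters. The change is normal with mean about zero. A smaller change SD (7-8) and a correlation of -0.3 between change and baseline serve as sensitivity cases.

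**Formulas.** Let p(b) be the chance of ending at 69 or better from baseline b. With change SD 9.5 and change independent of baseline, p(b) = Φ((b - 69)/9.5). For example, p(60) = Φ(-0.95) = 0.17, p(68) = Φ(-0.11) = 0.46 and p(73) = Φ(0.42) = 0.66. The first two share a stratum under either split; all three share one under the 74-letter split.

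- Two strata with shares W_k and mean rates p̄_k: V_S = Σ W_k p̄_k(1 - p̄_k)
- Continuous baseline: V_C = E[p(B)(1 - p(B))]
- Variance given up: r = 1 - V_C/V_S
- CI half-width: z √(V (1/251 + 1/167))

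**Central case (mean 74, SD 10, change SD 9.5).** V_S = 0.1730 (20/40 split) and 0.1733 (74-letter split); V_C = 0.1513. So r = 1 - 0.1513/0.1730 = 12.6%, and 12.7% for the other split. The half-width multiplier is 1.963 × √(1/251 + 1/167) = 0.196. The half-width is 0.196 × √0.1730 = 8.15 points with strata and 0.196 × √0.1513 = 7.62 points with continuous baseline, a gain of 0.53 points.

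**Range of r.**

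| Case | Against 20/40 split | Against 74-letter split |
|---|---|---|
| Change SD 9.5, mean 74, baseline SD 8 | 10.6% | 9.7% |
| Same, baseline SD 14 | 15.5% | 17.4% |
| Change SD 9.5, mean 70-76, baseline SD 8-14 | 9.4-15.7% | 8.8-19.1% |
| Change SD 7, mean 74, baseline SD 8-14 | 14.1-18.7% | 14.9-24.1% |
| Change SD 9.5, correlation -0.3, mean 70-76, baseline SD 8-14 | 5.5-13.0% | 4.9-15.8% |

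With baseline mean 72-76 and SD 9-12, change SD 7-9.5, and a slope of change on baseline from 0 to -0.2, the half-width gain is about 0.4-0.7 points against the 20/40 split and 0.3-0.9 against the 74-letter split. At correlation -0.3 with baseline SD 8 it is 0.2-0.3 points.

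**Simulation of the actual estimators** (418 patients, 3:2, randomisation stratified at 74, 8,000 runs, mean 74, baseline SD 8-14, change SD 9.5; CMH against a standardised logistic risk difference):

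| Reduction | Against 20/40 split | Against 74-letter split |
|---|---|---|
| Estimated variance (sets CI width) | 10.8-15.8% | 9.5-17.2% |
| True sampling variance | about 7-12% | about 10-17% |

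Against the 20/40 split the true gain is below the CI-width gain, because randomising within 74-letter strata already balances part of baseline.

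**The case against.** **Timing.** The rationale for this SAP version says that the Primary and Update CSRs were complete when it was written and that its changes concern data after Week 48. A reader might infer that the standardised estimate should replace CMH as the main analysis for both endpoints. The documents do not support that for the Week 36/40 average or visits through Week 48. Replacing a pre-specified main analysis after its results are reported is poor practice, however efficient the new model. This objection stands and limits the fix.

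**No decision depends on it.** Formal testing covers the primary endpoint and the three gated key secondary endpoints for the EMA. All are mean changes already adjusted for continuous baseline. The 69-letter endpoints have no margin, hypothesis or place in the testing order. This stands and keeps the severity minor.

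**Sample-size framing.** A reader might turn the variance into patients: 418 × (1/(1 - r) - 1) gives 41 at r = 9% and 105 at r = 20%. The documents do not support reading this as patients lost. The trial was sized on the primary endpoint, and 418 was reached by unintended over-enrolment above 360. CI width is the fair measure.

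**The plan already responds to baseline.** It does so for the Week 36/40 average, where the strata move to 20/40. It does not for the same threshold over time. CMH is also conventional and assumes little, which is a reason to keep it as a check.

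**The size is assumed.** That is true, so it is given as a range.

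**Conclusion.** The point holds as a small loss of precision. With baseline mean 70-76, baseline SD 8-14 and change SD 7-9.5, the two-level split gives up roughly 7-15% of the variance of the risk difference for the Week 36/40 average and 8-20% for the over-time version. A small change SD combined with a wide baseline goes above these ranges; strong regression to the mean takes the loss down to about 5%. In CI terms the half-width is about 0.3-0.9 percentage points wider than needed, on a base of about 8.

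A reader might infer that the CMH estimates are biased or that the non-inferiority or equivalence conclusion is weakened. Neither follows: CMH estimates a valid difference in proportions, and the formal tests use other models. Nor does the result extend to the change-based responder endpoints or the 38-letter endpoint, for which no gain is claimed.

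**What to change.** In SAP 4.4.2, fixed in writing before the final analysis:

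1. **Over-time 69-letter endpoint, visits after Week 48 (Final CSR).** Make the main estimate the risk difference from a logistic model fitted separately at each visit, with treatment, continuous baseline BCVA and the IxRS stratum, standardised over all patients. Give a delta-method or bootstrap 95.03% CI. Keep CMH over the 74-letter strata as the sensitivity analysis.
2. **Week 36/40 average and visits through Week 48.** Keep CMH as the main analysis and add the standardised estimate, labelled supportive and added after the results were reported.
3. **Missing visits.** State that the model is fitted to observed values and averaged over the Efficacy Population, which assumes missingness at random given arm and baseline. The carried-forward version stops at Week 40 and is unaffected.

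Standardising keeps the stated estimand, a difference in proportions. The cost is a short SAP edit and a few lines of code. The small downside is reliance on a working logistic model, which the retained CMH result checks.
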